8.4 Warnings and precautions

No evidence available at the time of the approval of this study protocol indicated that special warnings or precautions were appropriate, other than those noted in the provided [Investigator Brochure]. Additional safety information collected between IB updates will be communicated in the form of Investigator Notifications. This information will be included in the patient informed consent and should be discussed with the patient during the study as needed.

8.5 Data Monitoring Committee

A formal data monitoring board will not be used for this study. This is an open-label, Phase Ib/II study in which patients will receive MCS110 in combination with PDR001. Novartis will have access to the Safety Data on a regular basis. Novartis will host investigator teleconferences on a regular basis during the study. Further, during the Phase Ib part of the study, Novartis and the investigators will meet at the end of each treatment cohort to discuss and evaluate all of the gathered safety data. At the dose escalation teleconference the clinical course (safety information including both DLTs and all CTCAE Grade 2 or higher toxicity data during the first two cycles of treatment, and PK data) for each patient in the current dose cohort will be described in detail. Updated safety data on other ongoing patients, including data in later cycles, will be discussed as well.

Dose escalation decisions will be based on a clinical synthesis of all relevant available data and not solely on DLT information. Selection of the actual dose for the next cohort of patients will be guided by the BLRM with EWOC and a medical review of relevant clinical, PK and laboratory data. Novartis and the investigator parties must reach a consensus on whether to declare MTD, escalate the dose any further, or whether to de-escalate and/or recruit an additional cohort of patients at the current dose level ([Section 10.4.2](#)).

During the Phase II part of the study individual patient data will be reviewed on an ongoing basis. Overall response rate (ORR) for Group 1, 3, 4 and clinical benefit rate (CBR) for Group 2 per RECIST v1.1 and irRC and aggregate safety data will be monitored quarterly by the study team across the duration of the trial. Enrollment of each of Group 1, 3 and 4 will be expanded up to approximately 40 patients when objective responses (CR or PR) per RECIST v1.1 or irRC are observed (≥ 3 of 20 patients in each of the PD-1/PD-L1 therapy naïve groups or ≥ 2 of 20 patients in the PD-1/PD-L1 therapy resistant group). In Group 2, enrollment may be expanded up to approximately 40 patients at RP2D if clinical benefit per RECIST v1.1 or irRC (CR, PR or SD > 4 months) is observed in at least 3 pts. In addition, an exploratory group of 20 patients at a lower dose (1 mg/kg MCS110 in combination with PDR001 300 mg) may be opened if the above mentioned gating criteria is met (Group 2b). The decision of whether to expand a certain expansion group will be made at the time when the required number of responses is observed, or the last patient (out of 20 patients) has been on treatment for 6 months, whichever occurs earlier. The data review and analysis will be based on the available investigator reported data in the clinical database at that time [Section 10.7](#).

9 Data collection and management

9.1 Data confidentiality

Information about study subjects will be kept confidential and managed under the applicable laws and regulations. Those regulations require a signed subject authorization informing the subject of the following:

- What protected health information (PHI) will be collected from subjects in this study
- Who will have access to that information and why
- Who will use or disclose that information
- The rights of a research subject to revoke their authorization for use of their PHI.

In the event that a subject revokes authorization to collect or use PHI, the investigator, by regulation, retains the ability to use all information collected prior to the revocation of subject authorization. For subjects that have revoked authorization to collect or use PHI, attempts should be made to obtain permission to collect follow-up safety information (e.g. has the subject experienced any new or worsened AEs) at the end of their scheduled study period.

The data collection system for this study uses built-in security features to encrypt all data for transmission in both directions, preventing unauthorized access to confidential participant information. Access to the system will be controlled by a sequence of individually assigned user identification codes and passwords, made available only to authorized personnel who have completed prerequisite training.

Prior to entering key sensitive personally identifiable information (Subject Initials and exact Date of Birth), the system will prompt site to verify that this data is allowed to be collected. If the site indicates that country rules or ethics committee standards do not permit collection of these items, the system will not solicit Subject Initials. Year of birth will be solicited (in the place of exact date of birth) to establish that the subject satisfies protocol age requirements and to enable appropriate age-related normal ranges to be used in assessing laboratory test results.

9.2 Site monitoring

Before study initiation, at a site initiation visit or at an investigator's meeting, Novartis personnel (or designated CRO) will review the protocol and CRFs with the investigators and their staff. During the study, the field monitor will visit the site regularly to check the completeness of patient records, the accuracy of entries on the CRFs, the adherence to the protocol to Good Clinical Practice, the progress of enrollment, and to ensure that study treatment is being stored, dispensed, and accounted for according to specifications. Key study personnel must be available to assist the field monitor during these visits.

The investigator must maintain source documents for each patient in the study, consisting of case and visit notes (hospital or clinic medical records) containing demographic and medical information, laboratory data, electrocardiograms, and the results of any other tests or assessments. All information recorded on CRFs must be traceable to source documents in the patient's file. The investigator must also keep the original signed informed consent form (a signed copy is given to the patient).

The investigator must give the monitor access to all relevant source documents to confirm their consistency with the CRF entries. Novartis monitoring standards require full verification for the presence of informed consent, adherence to the inclusion/exclusion criteria and documentation of SAEs. Additional checks of the consistency of the source data with the CRFs are performed according to the study-specific monitoring plan.

9.3 Data collection

For studies using Electronic Data Capture (EDC), the designated investigator staff will enter the data required by the protocol into the Electronic Case Report Forms (eCRF). The eCRFs have been built using fully validated secure web-enabled software that conforms to 21 CFR Part 11 requirements, Investigator site staff will not be given access to the EDC system until they have been trained. Automatic validation programs check for data discrepancies in the eCRFs and, allow modification or verification of the entered data by the investigator staff.

The Principal Investigator is responsible for assuring that the data entered into eCRF is complete, accurate, and that entry and updates are performed in a timely manner.

PK [REDACTED] samples obtained during the course of the study will be collected from the Investigator sites and analyzed by a Novartis designated laboratory and/or contracted central laboratories. ECG data collected during the study will be reviewed locally by a cardiologist. During the course of the study, Novartis may decide to have a central review of the radiological assessments performed. In such case, the investigator's staff will be instructed on how to send data from these radiological assessments to a Contract Research Organization (CRO) for central review when needed. Designated investigational site

staff will enter the information required by the protocol into the appropriate eCRF and/or designated laboratory requisition forms. Field monitors will review the eCRFs and laboratory paper requisition forms for accuracy and completeness and instruct site personnel to make any required corrections or additions. One copy of the requisition form will be forwarded to each analytical laboratory with the respective sample(s) by the field monitor or by the designated investigational site staff; and one copy will be retained at the investigational site.

9.4 Database management and quality control

For studies using eCRFs, Novartis personnel will review the data entered by investigational staff for completeness and accuracy. Electronic data queries stating the nature of the problem and requesting clarification will be created for discrepancies and missing values and sent to the investigational site via the EDC system. Designated investigator site staff are required to respond promptly to queries and to make any necessary changes to the data.

Concomitant treatments and prior medications entered into the database will be coded using the WHO Drug Reference List, which employs the Anatomical Therapeutic Chemical classification system. Medical history/current medical conditions and adverse events will be coded using the Medical dictionary for regulatory activities (MedDRA) terminology.

Samples and/or data will be processed centrally and the results will be sent electronically to Novartis.

For EDC studies, after database lock, the investigator will receive a CD-ROM or paper copies of the patient data for archiving at the investigational site.

10 Statistical methods and data analysis

The data will be analyzed by Novartis and/or designated CRO. Any data analysis carried out independently by the investigator must be submitted to Novartis before publication or presentation.

It is planned that the data from participating centers in this protocol will be combined, so that an adequate number of patients will be available for analysis. The data will be summarized with respect to demographic and baseline characteristics, efficacy observations and measurements, safety observations and measurements, and all relevant PK and PD measurements using descriptive statistics (quantitative data) and contingency tables (qualitative data).

The study data will be analyzed and reported based on all patients' data of the Phase Ib and Phase II parts up to the time when all patients have potentially completed at least six cycles of treatment or discontinued the study. Any additional data for patients continuing to receive study treatment past the data cutoff date for the primary Clinical Study Report (CSR), as allowed by the protocol, will be reported at completion of the study as defined in [Section 4.3](#).

The following rules will be followed for reporting results unless stated otherwise:

- Phase Ib dose escalation data: cohorts treated during the dose escalation with the same dose levels of MCS110 and PDR001 will be pooled into a single treatment group. All summaries, listings, figures and analyses will be performed by treatment group.

- Phase II data: All summaries, listings, figures for non-safety analysis will be reported by group. Safety analysis of Phase II will be reported by group and all patients. For Group 2, all summaries, listings, figures will be reported by dose level, when applicable. The groups are the following:
 - Group 1: TNBC (naive to PD-1/PD-L1 directed therapy)
 - Group 2: Pancreatic cancer (naive to PD-1/PD-L1 directed therapy)
 - Group 3: Endometrial cancer (naive to PD-1/PD-L1 directed therapy)
 - Group 4: Melanoma (resistant to PD-1/PD-L1 directed therapy)

Categorical data will be presented as frequencies and percentages. For continuous data, mean, standard deviation, median, minimum, and maximum will be presented.

Screen failure patients are those who signed the informed consent, but never started the study treatment for any reason. For these patients, the eCRF data collected (see [Section 7.1.1.1](#)) will not be included in analyses, but will be reported in the CSR as separate listings.

10.1 Analysis sets

10.1.1 Full Analysis Set

The Full Analysis Set (FAS) comprises all patients who received at least one dose of MCS110 or PDR001. Patients will be analyzed according to the planned treatment combination. Unless otherwise specified, FAS is the default set used for all analyses.

10.1.2 Safety Set

The Safety Set (SS) includes all patients who have received at least one dose of MCS110 or PDR001. Patients will be classified according to treatment received, where treatment received is defined as:

1. The treatment assigned if it was received at least once, or
2. The first treatment received when starting therapy with study treatment if the assigned treatment was never received.

The safety set will be used for the safety summary of the study.

10.1.3 Per-Protocol Set

The Per Protocol Set (PPS) consists of a subset of FAS patients in the Phase II part who meet the following criteria:

- Presence of at least one measurable lesion according to RECIST v1.1 as per [Appendix 1](#)
- Have at least one post-baseline tumor assessment evaluable per RECIST v1.1, or have withdrawn due to clinical progression.
- Have received the planned treatment
- Have not been previously treated with PD-1 or PD-L1-directed therapy except patients in the melanoma pretreated group (Group 4), who must have previously received a PD-1 or PD-L1-directed therapy.

Patients will be classified according to planned treatment.

The PPS will be used in the Phase II part of the study only and will define the patients used in the sensitivity analysis of the primary endpoint [Section 10.4](#). If the PPS and the FAS are identical, then analyses described by the PPS below will not be performed.

10.1.4 Dose-determining analysis set

The DDS consists of all patients from the safety set in the Phase Ib dose escalation part who either meet the following minimum exposure criterion and have sufficient safety evaluations, or have experienced a DLT during first two cycles.

A patient is considered to have met the minimum exposure criterion if he/she received two doses of MCS110 and PDR001 during the first two cycles.

Patients who do not experience DLT during the first two cycles are considered to have sufficient safety evaluations if they have been observed for ≥ 42 days following the first dose, and are considered by both the Sponsor and Investigators to have enough safety data to conclude that a DLT did not occur.

Patients who do not meet these minimum safety evaluation requirements nor experience a DLT will be regarded as ineligible for the DDS and an additional patient may be recruited (see [Section 7.1.3.1](#)).

10.1.5 Pharmacokinetic analysis set

The Pharmacokinetic analysis set (PAS) includes all subjects who provide an evaluable PK profile. A profile is considered evaluable if all of the following conditions are satisfied:

- Subject receives the planned treatment
- Subject provides at least one primary PK parameter

Note: patients will be removed from the estimation of certain PK parameters on an individual basis depending on the number of available blood samples. These patients will be identified at the time of the analyses

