2.2.4 Pharmacokinetic Analysis Set

The pharmacokinetic analysis set (PAS) includes all patients who provide an evaluable PK profile. A profile is considered evaluable if all of the following conditions are satisfied:

- Patient receives one of the planned treatments
- Patient provides at least one primary PK parameter

Patients will be classified according to planned treatment group.

The PAS will be used for summaries of PK concentration data, PK parameters [REDACTED]

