2.4.1 Study treatment/compliance

Study treatment

MCS110 in combination with PDR001 (Q3W):

- Last date of *exposure* to study drug (MCS110) = last date of administration of MCS110 + 20 days
- Last date of *exposure* to study drug (PDR001) = last date of administration of PDR001 + 20 days
- Last date of *exposure* to study treatment (MCS110 + PDR001) = max (last date of MCS110 administration, last date of PDR001 administration) + 20 days = Date of last administration of study treatment + 20 days

Planned treatment: Planned treatment is the treatment to which a patient is assigned during enrollment.

Received treatment: Please refer to [Section 2.2.2](#).

Planned dose: Planned dose is the dose level(s) of study drug(s) corresponding to the planned treatment.

Prescribed dose: Prescribed dose is the dose level(s) of study drug(s) prescribed by doctor before study treatment is administered at beginning of each cycle.

Dose administered (mg/kg) for MCS110 = Dose prescribed (mg/kg) * Total volume administered (mL)/Total volume planned to be administered (mL);

Dose administered (mg) for PDR001 = Dose prescribed (mg) * Total volume administered (mL)/Total volume planned to be administered (mL);

Definitions of duration of exposure, cumulative dose, actual dose intensity (DI), planned dose intensity (PDI), relative dose intensity (RDI), as well as intermediate calculations, are as follows:

- **Duration of exposure (days) to study drug:** last date of *exposure* to study drug – first date of study drug + 1 (periods of interruption are not excluded);

- **Duration of exposure (days) to study treatment:** last date of *exposure* to study treatment – first date of study treatment + 1 (periods of interruption are not excluded);
- **Duration of exposure (weeks)** = Duration of exposure (days)/7;
- **Cumulative dose:** sum of all dose administered (mg/kg) to a patient for MCS110; sum of all dose administered (mg) to a patients for PDR001;
- **Cumulative planned dose:** sum of all planned dose (mg/kg) of MCS110 that were intended to have been taken during the treatment period by a patient; sum of all planned dose (mg) of PDR001 that were intended to have been taken during the treatment period by a patient;

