2.9 Pharmacokinetics Analyses

The pharmacokinetic parameters will be determined by profiles using noncompartmental method(s) for both MCS110 and PDR001 as presented in [Table 2-5](#), and PAS will be used in all pharmacokinetic data analysis and PK summary statistics. Patients will be removed from the estimation of certain PK parameters on an individual basis depending on the number of available blood samples. These patients will be identified at the time of the analyses.

Table 2-5 Pharmacokinetic parameters to be analyzed

AUClast	The AUC from time zero to the last measurable concentration sampling time (tlast) (mass \times time \times volume ⁻¹)
AUCinf	The AUC from time zero to infinity (mass \times time \times volume ⁻¹)
Cmax	The maximum (peak) observed plasma, blood, serum, or other body fluid drug concentration after single dose administration (mass \times volume ⁻¹)
Tmax	The time to reach maximum (peak) plasma, blood, serum, or other body fluid drug concentration after single dose administration (time)
T1/2	The terminal half-life associated with the terminal slope (λ_z) of a semi logarithmic concentration-time curve (time). Use qualifier for other half-lives
CL	The total body clearance of drug from the plasma (volume \times time ⁻¹)
Vz	The apparent volume of distribution during terminal phase (associated with λ_z) (volume)
Clast	Last observed quantifiable concentration (mass \times volume ⁻¹)
AR	Accumulation Ratio=AUClast (multiple Dose)/AUClast (single dose) (for cycle 4 only)

For phase Ib part, descriptive statistics of all pharmacokinetic parameters in the [Table 2-5](#) for both cycle 1 and cycle 4 will include arithmetic and geometric mean, median, SD, and CV, geometric CV, minimum and maximum, by treatment group. For phase II part, descriptive statistics will be conducted for the parameters, including AUClast, AUCinf, Cmax, Clast, Tmax for both cycle 1 and cycle 4 and AR only for cycle 4 by patient group.

Summary statistics will be presented for MCS110 and PDR001 serum concentrations at each scheduled time point. Descriptive graphical plots of individual and mean serum/plasma concentration versus time profiles of free MCS110, PDR001 will be generated by treatment or patient group and cycle.

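### No rule ties a cycle 4 PK profile to the dose given in that cycle, so profiles taken after a dose reduction are summarised under the dose planned at enrollment

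*Protocol*

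**What the plan says.** Protocol 10.1.5 sets two conditions for an evaluable profile: "Subject receives the planned treatment", and the subject provides at least one primary PK parameter. It gives no rule for classifying patients.

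SAP 2.2.4 words the first condition as "Patient receives one of the planned treatments" and adds that "Patients will be classified according to planned treatment group". SAP 2.4.1 defines the term: "Planned treatment is the treatment to which a patient is assigned during enrollment". The label therefore does not follow later dose changes.

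SAP 2.9 plans Phase Ib parameter summaries "for both cycle 1 and cycle 4 will include arithmetic and geometric mean, median, SD, and CV", then geometric CV, "minimum and maximum, by treatment group". Phase II parameters are summarised for the same two cycles by patient group. The accumulation ratio in SAP Table 2-5 compares AUClast at cycle 4 with the single-dose value and has no dose term. Protocol Table 10-1 defines the ratio on Cmax instead, also without a dose term.

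Two removal rules are visible. SAP 2.9 states that "Patients will be removed from the estimation of certain PK parameters on an individual basis depending on the number of available blood samples", which matches the note in protocol 10.1.5. SAP Table 5-3 excludes from the PK set only patients with no primary PK parameter.

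**The concern.** The plan foresees dose reductions before cycle 4. Under protocol 6.3.1, a patient who resumes after an event meeting DLT criteria does so at the next lower level. That can happen within cycles 1 and 2, and other adjustments are allowed afterwards. Table 6-4 lowers MCS110 by one level for certain CK elevations and for Grade 2 periorbital edema. Section 6.2.3.2 bars increases in the first 6 months. Changes of dose level before cycle 4 can therefore only go downward, and they occur in patients who had toxicity.

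Followed literally, the SAP reports such a patient's cycle 4 AUC and Cmax at a dose the patient no longer receives. Its accumulation ratio divides a reduced-dose exposure by a full-dose exposure. Characterising the PK of both drugs is a secondary objective, and the Phase Ib results are presented by dose level. Exposure at the planned dose and accumulation would both be understated.

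SAP 2.5.2.1.1 already has a rule for the dose-toxicity model when a patient's first two doses differ. The PK sections have no counterpart.

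**Working it through.** The documents give no figure on this point, so there is none to reproduce. The check has two parts.

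**1. Following a reduced-dose profile through the rules**

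- Protocol condition: a patient given the assigned dose in cycle 1 has received the planned treatment. The text does not require this at each cycle.
- SAP condition: met on the same facts.
- Classification: the group assigned at enrollment.
- Removal: sample count or absence of a primary parameter. Dose plays no part.
- Protocol 7.2.3: shifts sampling if the cycle 4 dose is delayed, but does not mention a reduced dose.
- Accumulation ratio: no dose normalisation.

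The profile stays in the original group.

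**2. Size, as an illustration**

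*PDR001.* Inputs: half-life T of 20 days, 90% CI 17 to 23 (protocol, Amendment 01 rationale); 21-day cycle; 300 and 100 mg levels (Table 6-2). Assumptions: linear one-compartment PK, and AUClast taken over the same span in both cycles.

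- Fraction remaining after one cycle: r = exp(−ln 2 × 21/T). With T = 20, r = 0.483, r² = 0.233 and r³ = 0.113.
- Ratio: AR = sum over doses i = 1 to 4 of (relative dose × r^(4−i)).
- Constant dose: 1 + 0.483 + 0.233 + 0.113 = 1.83. For T = 17 to 23 the range is 1.68 to 1.96.
- 300 mg in cycle 1, then 100 mg from cycle 2: 0.113 + (0.233 + 0.483 + 1)/3 = 0.68. The range is 0.61 to 0.75.

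In Table 6-2 the only one-level step that lowers PDR001 is from 3 mg/kg with 300 mg to 3 mg/kg with 100 mg. The Amendment 04 study status gives 12 patients at 3 mg/kg with 300 mg. With one of 12 reduced and all contributing, the geometric mean is 1.83 × (0.68/1.83)^(1/12) = 1.83 × 0.92, or about 1.69. That is a fall of about 8%. The multiplier is also 0.92 at both ends of the half-life interval.

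*MCS110.* No half-life for this drug is used here, so the calculation rests on dose proportionality alone. One patient's cycle 4 exposure, and hence the ratio, is multiplied by reduced dose / original dose. Group sizes are again from the Amendment 04 status; 7.5 mg/kg is a level added during the study.

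| Step (mg/kg) | Patient multiplier | Patients in group | Geometric mean multiplier, one reduced |
|---|---|---|---|
| 10 to 5 | 0.50 | 11 | 0.50^(1/11) = 0.94 |
| 7.5 to 5 | 0.67 | 6 | 0.67^(1/6) = 0.93 to 0.94 |
| 5 to 3 | 0.60 | 13 | 0.60^(1/13) = 0.96 |

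Two departures from proportionality pull in opposite directions. Section 1.2.2.2.1 of the protocol reports clearance falling as dose rises, so exposure may drop by more than the dose. Drug left over from earlier full doses makes the drop smaller.

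**The case against.** The strongest objection concerns the cause. Setting "Subject receives the planned treatment" beside "Patient receives one of the planned treatments", a reader might infer that the SAP loosened a protocol rule that would have kept these profiles out. The documents do not support that. The protocol condition is per subject and would not clearly exclude them either. The SAP plural may only reflect that Phase Ib has several dose combinations. The absence of this wording from SAP section 4 is weak evidence, because that section says it records updates since the first SAP, which is not available. What remains is classification by planned group with no dose rule, and that stands under either wording.

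A reader might also infer a larger effect, for example from a halved PDR001 dose or from one reduced patient in a group of six (1.83 × (0.68/1.83)^(1/6) = 1.55). A halved PDR001 dose is not a listed level. The groups of six were 1 mg/kg with 100 mg and 7.5 mg/kg with 300 mg, where a one-level step leaves PDR001 unchanged. The figure of 1.55 would need only 6 of the 12 patients at 3 mg/kg with 300 mg to contribute, and the documents give no such count.

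Nor do the documents show harm to this trial's dose choice. Amendment 04 gives the RP2D as 7.5 mg/kg of MCS110, and Amendment 05 reports enrollment closed. No visible section plans a dose-proportionality analysis.

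Other points stand in part. Most entries in Table 6-4 resume at the same dose or stop treatment, so reductions may be few. SAP 2.4.1 lists all doses with reasons for change, so affected patients can be traced. Part of the SAP text on use of the PK set is redacted, derivations sit in a separate programming document, and protocol 10.5.4 allows a separate PK plan, so a rule may exist elsewhere. None of this changes what the stated rules do.

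**Conclusion.** The point holds as a gap in the PK rules. Planned-group classification, without any rule on the dose given in the profiled cycle, places reduced-dose cycle 4 profiles in the original dose's Phase Ib summaries and in the Phase II disease-group summaries. It also lets them into an accumulation ratio that is not dose-normalised. The direction is downward and the route is through patients with toxicity.

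The size is modest and uncertain. One PDR001 reduction among 12 patients moves the geometric mean ratio from 1.83 to about 1.69, given linear PK, a 20-day half-life, a reduction from cycle 2 and all 12 contributing. An MCS110 step from 10 to 5 mg/kg roughly halves that patient's cycle 4 exposure under dose proportionality, possibly more given dose-dependent clearance. The documents do not say how many cycle 4 profiles followed a reduction. The outputs affected are descriptive.

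Two side points need reconciling: the differing wording of the PK set condition, and the accumulation ratio on Cmax in the protocol against AUClast in the SAP.

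**What to change.** In SAP 2.2.4 and 2.9, decide inclusion per profile and per drug:

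- A cycle 4 profile or concentration enters a dose group's summary only if the dose of that drug given on Day 1 of the cycle was the planned dose.
- The accumulation ratio is computed only when the cycle 1 to 4 doses of that drug were all given at the same level.
- Remaining profiles are listed, or summarised, by the dose actually given.
- In Phase II the same flag is applied within each disease group.

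Align the PK set condition with protocol 10.1.5, choose one definition of the accumulation ratio, and record these changes in SAP section 4.

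The cost is SAP wording and one derived flag from dosing records already collected. The downside is slightly fewer cycle 4 profiles per group.
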